10.4.2. Treatment Emergent Flag for Adverse Events

Flag	Definition
Treatment Emergent	• If AE onset date is on or after treatment start date & on or before treatment stop date +1.
	 Study Treatment Start Date ≤ AE Start Date ≤ Study Treatment Stop Date + 1 days.
	• For studies with greater than one treatment period (e.g., crossover study), if AE onset is during one period and worsens during a later period it would be counted in both periods. For the initial period the logic would be as above. For the later period the logic would use the treatment dates associated with the later period:
	Treatment Period Start Date \leq AE Worsening Date \leq Study Treatment Stop Date + 1 days.

NOTES:

• If the study treatment stop date is missing, then the AE will be considered to be Treatment Emergent.

• Time of study treatment dosing and start/stop time of AEs should be considered, if collected.

10.5. Appendix 5: Data Display Standards & Handling Conventions

10.5.1. Reporting Process

Software	Software							
The currently supported versions of SAS software will be used.								
Reporting Area	Reporting Area							
HARP Server	: UK1SALX00175							
HARP Compound	One reporting effort will be set up for this study which combines Part A and Part B: \ arenv \ arprod \ gsk2982772 \ mid205184 \final_01							
Analysis Datasets								
 Analysis datasets will be created according to Integrated Data Standards Library (IDSL) GSK A&R dataset standards 								
Generation of RTF Files								
 RTF files will be generated for all tables within the final_01 reporting effort. 								

10.5.2. Reporting Standards

General

• The current GSK Integrated Data Standards Library (IDSL) will be applied for reporting, unless otherwise stated (IDSL Standards Location: https://spope.gsk.com/sites/IDSLLibrary/SitePages/Home.aspx):

- 4.03 to 4.23: General Principles
- 5.01 to 5.08: Principles Related to Data Listings
- 6.01 to 6.11: Principles Related to Summary Tables
- 7.01 to 7.13: Principles Related to Graphics
- Do not include participant level listings in the main body of the GSK Clinical Study Report. All participant level listings should be located in the modular appendices as ICH or non-ICH listings.
- All data displays (Tables, Figures & Listings) will use the term "Subject" which reflects CDISC and GSK Data Display Standards terminology.

Formats

- All data will be reported according to the actual treatment the participant received, unless otherwise stated.
- GSK IDSL Statistical Principles (5.03 & 6.06.3) for decimal places (DP's) will be adopted for reporting of data based on the raw data collected, unless otherwise stated.
- Numeric data will be reported at the precision collected on the eCRF.
- The reported precision from non eCRF sources will follow the IDSL statistical principles but may be adjusted to a clinically interpretable number of DP's.

Planned and Actual Time

- Reporting for tables and figures:
 - Planned time relative to dosing will be used in figures and summaries and calculation of any derived parameters, unless otherwise stated.
 - The impact of any major deviation from the planned assessment times and/or scheduled visit days on the analyses and interpretation of the results will be assessed as appropriate.
- Reporting for Data Listings:
 - Planned and actual time relative to study drug dosing will be shown in listings (Refer to IDSL Statistical Principle 5.05.1).

Unscheduled	Unscheduled or unplanned readings will be presented within the participant's listings.								
Unscheduled Visits									
Unscheduled visi	 Unscheduled visits will not be included in summary tables and/or figures. 								
All unscheduled v	All unscheduled visits will be included in listings.								
Descriptive Summar	y Statistics								
Continuous Data	Refer to IDSL Statistical Principle 6.06.1								
Categorical Data	N, n, frequency, %								
Graphical Displays									
Refer to IDSL Statistical Principals 7.01 to 7.13.									

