9. STUDY ASSESSMENTS AND PROCEDURES

- Study procedures and their timing are summarized in the SoA.
- Protocol waivers or exemptions are not allowed.
- Immediate safety concerns should be discussed with the sponsor immediately upon occurrence or awareness to determine if the participant should continue or discontinue study treatment.
- Adherence to the study design requirements, including those specified in the SoA, is essential and required for study conduct.
- All screening evaluations must be completed and reviewed to confirm that potential participants meet all eligibility criteria. The investigator will maintain a screening log to record details of all participants screened and to confirm eligibility or record reasons for screening failure, as applicable.
- Procedures conducted as part of the participant's routine clinical management (e.g., blood count) and obtained before signing of ICF may be utilized for screening or baseline purposes provided the procedure met the protocol-specified criteria and was performed within the time frame defined in the SoA.
 - The maximum amount of blood collected from each participant over the duration of the study, including any extra assessments that may be required, will not exceed 500 mL.
 - Repeat or unscheduled samples may be taken for safety reasons or for technical issues with the samples.

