9.3.5. Clinical Safety Laboratory Assessments

- Refer to [Appendix 2](#) for the list of clinical laboratory tests to be performed and to the SoA for the timing and frequency.
- The investigator must review the laboratory report, document this review, and record any clinically relevant changes occurring during the study in the AE section of the CRF. The laboratory reports must be filed with the source documents. Clinically significant abnormal laboratory findings are those which are not associated with the underlying disease, unless judged by the investigator to be more severe than expected for the participant's condition.
- All laboratory tests with values considered clinically significantly abnormal during participation in the study should be repeated until the values return to normal or baseline or are no longer considered significantly abnormal by the investigator or medical monitor.
- If such values do not return to normal/baseline within a period of time judged reasonable by the investigator, the etiology should be identified and the sponsor notified.
- All protocol-required laboratory assessments, as defined in [Appendix 2](#), must be conducted in accordance with the SRM and the SoA.

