
liver event follow up assessments within 24-72 hr
 
 • Monitor subjects weekly until liver chemistries resolve, stabilize or return to within baseline 	
antibody, Type 1 anti-liver kidney microsomal antibodies, and quantitative total immunoglobulin G (IgG) or gamma globulins.
 
 • Serum acetaminophen adduct high performance liquid chromatography (HPLC) assay (quantifies potential acetaminophen contribution to liver injury in subjects with definite or likely acetaminophen use in the preceding week [James, 2009]. NOTE: not required in China. • Liver imaging (ultrasound, magnetic resonance, or computerised tomography) and /or liver biopsy to evaluate liver disease; complete Liver Imaging and/or Liver Biopsy CRF forms.

1. Serum bilirubin fractionation should be performed if testing is available. If serum bilirubin fractionation is not immediately available, discontinue study treatment for that subject if ALT \geq 3xULN and bilirubin \geq 2xULN. Additionally, if serum bilirubin fractionation testing is unavailable, record presence of detectable urinary bilirubin on dipstick, indicating direct bilirubin elevations and suggesting liver injury.
2. All events of ALT \geq 3xULN and bilirubin \geq 2xULN (>35% direct bilirubin) or ALT \geq 3xULN and INR>1.5, if INR measured, which may indicate severe liver injury (possible 'Hy's Law'), must be reported as an SAE (excluding studies of hepatic impairment or cirrhosis); INR measurement is not required and the threshold value stated will not apply to subjects receiving anticoagulants
3. Includes: Hepatitis A IgM antibody; Hepatitis B surface antigen and Hepatitis B Core Antibody (IgM); Hepatitis C RNA; Cytomegalovirus IgM antibody; Epstein-Barr viral capsid antigen IgM antibody (or if unavailable, obtain heterophile antibody or monospot testing); Hepatitis E IgM antibody
4. PK sample may not be required for subjects known to be receiving placebo or non-GSK comparator treatments. Record the date/time of the PK blood sample draw and the date/time of the last dose of study treatment prior to PK blood sample draw on the CRF. If the date or time of the last dose is unclear, provide the subject's best approximation. If the date/time of the last dose cannot be approximated OR a PK sample cannot be collected in the time period indicated above, do not obtain a PK sample. Instructions for sample handling and shipping are in the SRM.

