10.3. Appendix 3: Assessment Windows

10.3.1. Definitions of Assessment Windows for Analyses

No Assessment Windows will be defined for Analysis, and summaries and analyses will be based on nominal visits.

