10.6. Appendix 6: Derived and Transformed Data

10.6.1. General

Multiple Measurements at One Analysis Time Point

- Mean of the measurements will be calculated and used in any derivation of summary statistics but if listed, all data will be presented except for blood pressure measurements as only the average of the 3 blood pressure readings will be recorded on the CRF.
- If there are two values within a time window the value closest to the target day for that window will be used. If values are the same distance from the target, then the mean will be taken.
- Participants having both High and Low values for Normal Ranges at any post-baseline visit for safety parameters will be counted in both the High and Low categories of "Any visit post-baseline" row of related summary tables. This will also be applicable to relevant Potential Clinical Importance summary tables.

Study Day

- Calculated as the number of days from First Dose Date:
 - Ref Date = Missing \rightarrow Study Day = Missing
 - Ref Date < First Dose Date \rightarrow Study Day = Ref Date First Dose Date
 - Ref Data ≥ First Dose Date → Study Day = Ref Date (First Dose Date) + 1

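### Leaving unscheduled visits out of every summary table and figure lets the worst-case laboratory, hepatobiliary and maximum ALT/bilirubin displays (and, less certainly, the maximum-QTc tables) understate a participant's worst post-baseline value

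*SAP*

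**What the plan says.** Four SAP provisions bear on this.

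- **10.5.2, unscheduled visits:** "Unscheduled visits will not be included in summary tables and/or figures". They go into listings. A separate line says unscheduled readings are shown in the participant listings.
- **10.5.2, general:** the sponsor's display standards (IDSL) "will be applied for reporting, unless otherwise stated", so they give way where the SAP says something different.
- **10.3.1:** "No Assessment Windows will be defined for Analysis, and summaries and analyses will be based on nominal visits".
- **10.6.1:** participants with both high and low values "at any post-baseline visit for safety parameters will be counted in both the High and Low categories" of an any-visit post-baseline row.

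SAP 10.10.5 and 10.10.6 plan worst-case chemistry, lipid, haematology and urinalysis tables, hepatobiliary abnormality tables, maximum-QTc tables, and plots of maximum ALT and bilirubin. None carries a programming note that brings unscheduled values back.

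The protocol expects off-schedule data. Section 9: "Repeat or unscheduled samples may be taken for safety reasons or for technical issues with the samples". Section 9.3.5: clinically significant laboratory values "should be repeated until the values return to normal or baseline". Appendix 7, for ALT ≥3×ULN without raised bilirubin or INR, asks for repeat chemistries and "liver event follow up assessments within 24-72 hr", then: "Monitor subjects weekly until liver chemistries resolve, stabilize or return to within baseline".

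**The concern.** A table titled as worst case, or a figure of maxima, should hold each participant's most extreme post-baseline value. Under 10.5.2 it holds the most extreme scheduled value. The omitted readings are not a random subset: under 9.3.5 and Appendix 7 they are taken because something was abnormal. Baseline is treated differently, since SAP 5.2 takes the latest pre-dose value including unscheduled ones. An off-schedule reading can therefore set the baseline but not the post-baseline extreme.

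Laboratory values and 12-lead ECG are primary endpoints. At stake are the threshold counts and plotted maxima in the main body of the study report, where 10.5.2 does not allow participant listings to appear.

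**Working it through.** **1. Displays affected.**
- Laboratory and liver tables: 2.8, 2.11, 2.12, 2.14, 2.28, 2.29, 2.31, 2.32, 2.34 = 9. Table 2.9 (Part A lipids) is left out because Protocol Appendix 2 lists lipids for Part B only.
- ALT/bilirubin figures: 2.2, 2.3, 2.5, 2.6 = 4.
- QTc tables, less certain: 2.16, 2.18, 2.37, 2.39 = 4.

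**2. Scheduled chemistry, Part B (SAP 10.2.1.2).** After baseline: Days 2, 4, 7, 10, 15 and follow-up. Follow-up is 7 to 14 days after the last dose (Protocol synopsis). With the last dose on Day 14, that is Day 14 + 7 = 21 to Day 14 + 14 = 28. The gap after Day 15 is 21 − 15 = 6 to 28 − 15 = 13 days.

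**3. Off-schedule draws after a Day 15 ALT-only trigger (Appendix 7).**
- Repeat at 24–72 hr: Day 16 to Day 18, 1 draw.
- Weekly draw: Day 22 if counted from Day 15, or Day 23–25 if counted from the repeat. That gives 0 or 1 before follow-up; a second would fall on Day 29 or later.
- Total: 1 to 2 draws absent from Table 2.34 and Figures 2.5 and 2.6.
- If the repeat itself shows bilirubin ≥2×ULN or INR >1.5, monitoring becomes twice weekly. From the repeat, 21 − 18 = 3 to 28 − 16 = 12 days remain. 3/3.5 = 0.9 and 12/3.5 = 3.4, so 0 to 3 whole draws follow the repeat.

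**4. How a maximum plot changes (invented values).** Day 15: ALT 3.1×ULN, bilirubin 1.2×ULN. Off-schedule repeat: 5.8 and 2.2. Follow-up: 1.4 and 1.1. With scheduled visits only, Figure 2.6 plots (3.1, 1.2). With all post-baseline values it plots (5.8, 2.2), which passes bilirubin 2×ULN together with ALT 3×ULN.

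**5. Effect on a count.** Protocol 10.1 plans at most 9 per active dose and gives exact 95% upper limits of 33.6% at 0/9 and 48.2% at 1/9. The Clopper–Pearson upper limit, the 0.975 quantile of Beta(x+1, n−x), gives 33.63% and 48.25%, so the plan's figures reproduce. One crossing seen only off-schedule changes 1/9 = 11.1% to 0/9, and the upper limit falls from 48.2% to 33.6%.

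SAP 5.1 gives Cohorts 2 and 3 the same 120 mg TID label. If they are pooled, n = 9 + 1 to 9 = 10 to 18, because the documents do not say how many Cohort 2 participants beyond the sentinels received active drug. The shift is then 1/10 = 10.0 to 1/18 = 5.6 points.

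**6. How often.** The documents do not say. If each of two true crossers crosses only off-schedule with assumed probability q, the chance of missing at least one is 1 − (1 − q)²: 19% at q = 0.10, 44% at 0.25, 75% at 0.50.

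**The case against.** **10.6.1 says any post-baseline visit.** It is the more specific text for these tables, and the SAP states no order of precedence. But the sentence settles how to count someone with both a high and a low value. It does not say unscheduled visits count, whereas 10.5.2 says they do not.

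**The IDSL shells are not in the documents and may include unscheduled values.** They may. They would then conflict with a rule that the SAP states outright, and IDSL yields to the SAP.

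**Visits are not readings.** This partly stands. 10.5.2 bars unscheduled visits, and Part B participants are inpatients until Day 17. A repeat on Day 16 or 17 is an unscheduled reading but not clearly an unscheduled visit. The nominal-visit rule in 10.3.1 makes exclusion probable, not certain.

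**The QTc case is weak.** This stands in part. Protocol 8.1.4 exempts safety and non-protocol ECGs from the single-formula rule, which can be read as placing them outside the analysis data. Confirmatory ECGs minutes after a prolonged reading may already be averaged under 10.6.1. No QTc magnitude can be given.

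**The harm is small.** Largely true. No hypotheses are tested. Unscheduled data are listed, clinically significant findings are adverse events, and Tables 2.13 and 2.33 report liver stopping events, though their data source is not stated. None of these corrects the counts or the plotted maxima.

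**Scheduled-only summaries keep the number of readings comparable.** A fair point of design. It suits by-visit means better than displays that claim to show an extreme.

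**Conclusion.** The concern holds for the worst-case laboratory tables, the hepatobiliary tables and the maximum ALT/bilirubin figures, and less certainly for the maximum-QTc tables. As written, these displays can understate a participant's worst post-baseline value. In the Day 15 example, 1 to 2 required draws are missed and one participant in 9 can drop out of a count. This assumes that Appendix 7 follow-up applies to a trigger seen the day after the last dose, that repeats during the inpatient stay fall under the exclusion, and that the crossing appears at no scheduled visit.

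Three stronger readings are not supported:

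- **That the data are lost, or a signal is hidden.** Every unscheduled visit is listed, and an abnormality still present at a scheduled visit is counted at its scheduled value.
- **That the study's results will be understated.** The documents give no count of unscheduled readings, so the size is an illustration.
- **That a Day 10 ALT trigger shows the same fixed gap to Day 15.** Appendix 7 stops treatment at once, and the documents do not say that an early stopper still has the Day 15 visit. With a last dose on Day 10, follow-up would fall on about Day 17–24. The next scheduled chemistry is therefore not fixed.

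**What to change.** Replace the sentence in SAP 10.5.2 with: *Unscheduled visits and readings are excluded from by-visit summaries only; they are included in all worst-case, maximum and any-visit post-baseline derivations.* Name the displays: Tables 2.8, 2.11, 2.12, 2.14, 2.28, 2.29, 2.31, 2.32 and 2.34, and Figures 2.2, 2.3, 2.5 and 2.6. Naming readings as well as visits removes the inpatient ambiguity.

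Apply the same rule to Tables 2.16, 2.18, 2.37 and 2.39, with unscheduled ECGs entering as QTcF, recorded or derived under 10.6.3. State that confirmatory ECGs taken within minutes of a triggering ECG are averaged with it as one time point under 10.6.1, in line with Protocol 8.1.4.

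The cost is two or three sentences and a derivation flag. The data are already destined for the listings, so nothing new is collected. One small downside deserves a footnote: participants with triggered repeats contribute more readings to their maximum than others do.

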10.5.3. Reporting Standards for Pharmacokinetic

Pharmacokinetic Con	centration Data
PC Windows Non- Linear (WNL) File	PC WNL file (CSV format) for the non-compartmental analysis by Clinical Pharmacology Modelling and Simulation function will be created according to PKOne. Note: Concentration values will be imputed as per GUI_51487.
Descriptive Summary Statistics, Graphical Displays and Listings	Refer to IDSL PK Display Standards. Refer to IDSL Statistical Principle 6.06.1. Note: Concentration values will be imputed as per GUI_51487 for descriptive summary statistics/analysis and summarized graphical displays only.
Pharmacokinetic Para	ameter Derivation
PK Parameter to be Derived by Programmer	The following PK parameters will be derived by the Programmer: $C_0,C_7,C_{12},C_{14},C_{24}.$
Pharmacokinetic Para	ameter Data
Is NQ impacted PK Parameters Rule Being Followed	Yes, refer to Standards for Handling NQ Impacted PK Parameters.
Descriptive Summary Statistics, Graphical Displays and Listings	Refer to IDSL PK Display Standards. Refer to PKOne.

10.6. Appendix 6: Derived and Transformed Data

10.6.1. General

Multiple Measurements at One Analysis Time Point

- Mean of the measurements will be calculated and used in any derivation of summary statistics but if listed, all data will be presented except for blood pressure measurements as only the average of the 3 blood pressure readings will be recorded on the CRF.
- If there are two values within a time window the value closest to the target day for that window will be used. If values are the same distance from the target, then the mean will be taken.
- Participants having both High and Low values for Normal Ranges at any post-baseline visit for safety parameters will be counted in both the High and Low categories of "Any visit post-baseline" row of related summary tables. This will also be applicable to relevant Potential Clinical Importance summary tables.

Study Day

- Calculated as the number of days from First Dose Date:
 - Ref Date = Missing \rightarrow Study Day = Missing
 - Ref Date < First Dose Date \rightarrow Study Day = Ref Date First Dose Date
 - Ref Data ≥ First Dose Date → Study Day = Ref Date (First Dose Date) + 1

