Part B	Cohorts 2, 3, 4	and 5 – repeat do	se, sequential-group): Laboratory: Chemistry		
2.27.	Safety (Part B)	LB1	Summary of Chemistry Changes from Baseline (Part B)	ICH E3	SAC
2.28.	Safety (Part B)	LB17	Summary of Worst Case Chemistry Results by PCI Criteria Post-Baseline Relative to Baseline (Part B)	ICH E3	SAC
2.29.	Safety (Part A)	LB17	Summary of Worst Case Lipids Outside Laboratory Normal Range Post-Baseline Relative to Baseline (Part B)		SAC
Part B	Cohorts 2, 3, 4	and 5 – repeat do	se, sequential-group): Laboratory: Hematology		
2.30.	Safety (Part B)	LB1	Summary of Hematology Changes from Baseline (Part B)	ICH E3	SAC
2.31.	Safety (Part B)	LB17	Summary of Worst Case Hematology Results by PCI Criteria Post-Baseline Relative to Baseline (Part B)	ICH E3	SAC
Part B	Cohorts 2, 3, 4	and 5 – repeat do	se, sequential-group): Laboratory: Urinalysis		
2.32.	Safety (Part B)	UR1	Summary of Worst Case Urinalysis Results (Discrete or Character Values) Post-Baseline Relative to Baseline (Part B)	ICH E3	SAC
Part B	Cohorts 2, 3, 4	and 5 – repeat do	se, sequential-group): Laboratory: Hepatobiliary (Liver)	·	
2.33.	Safety (Part B)	LIVER1	Summary of Liver Monitoring/Stopping Event Reporting (Part B)	IDSL	SAC
2.34.	Safety (Part B)	LIVER10	Summary of Hepatobiliary Laboratory Abnormalities (Part B)	IDSL	SAC

Safety:	Safety: Tables					
No.	Population	IDSL / Example Shell	Title	Programming Notes	Deliverable [Priority]	
Part B	(Cohorts 2, 3, 4	and 5 – repeat do	se, sequential-group): Laboratory: Other			
2.35.	Pharmacoki netic (Part B)	Non-Standard SAFE_T1	Summary of Plasma 4 β -hydroxycholesterol to Cholesterol Ratio (Part B)	Include SE and 95% CI.	SAC	
Part B	(Cohorts 2, 3, 4	and 5 – repeat do	se, sequential-group): ECG			
2.36.	Safety (Part B)	EG1	Summary of ECG Findings (Part B)	IDSL	SAC	
2.37.	Safety (Part B)	EG10	Summary of Maximum QTc Values Post-Baseline Relative to Baseline by Category (Part B)	IDSL	SAC	
2.38.	Safety (Part B)	EG2	Summary of Change from Baseline in ECG Values by Visit (Part B)	IDSL	SAC	
2.39.	Safety (Part B)	EG11	Summary of Maximum Increase in QTc Values Post-Baseline Relative to Baseline by Category (Part B)	IDSL	SAC	
Part B	(Cohorts 2, 3, 4	and 5 – repeat do	se, sequential-group): Vital Signs			
2.40.	Safety (Part B)	VS1	Summary of Change from Baseline in Vital Signs (Part B)	ICH E3	SAC	
Part B	(Cohorts 2, 3, 4	and 5 – repeat do	se, sequential-group): Suicide Risk Monitoring			

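### As written, SAP 10.6.1 can average an abnormal laboratory value with a repeat at the same time point before the worst-case laboratory summaries, so a crossed flag can be lost

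*SAP*

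**What the plan says.** SAP 10.6.1 has three rules for multiple measurements at one analysis time point.

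- The first is "Mean of the measurements will be calculated and used in any derivation of summary statistics", with an exemption for listings, which show every value. Its only further qualification concerns blood pressure, for which the CRF holds just the average of three readings.
- The second is "If there are two values within a time window the value closest to the target day for that window will be used".
- The third counts a participant with both high and low values under both categories, and adds "This will also be applicable to relevant Potential Clinical Importance summary tables".

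Three other SAP rules bear on this. Section 5.2 already provides separately for the mean of triplicates. Section 10.3.1 defines no assessment windows and works from nominal visits. Section 10.5.2 sends unscheduled or unplanned readings to the listings and states "Unscheduled visits will not be included in summary tables and/or figures".

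On repeats, protocol 9.3.5 says "All laboratory tests with values considered clinically significantly abnormal during participation in the study should be repeated until the values return to normal"; a return to baseline, or a judgement that the value has ceased to be significant, also ends them. Protocol section 9 adds "Repeat or unscheduled samples may be taken for safety reasons or for technical issues with the samples".

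The display list in SAP 10.10.5 includes "Summary of Worst Case Chemistry Results by PCI Criteria" for each part (Tables 2.8 and 2.28), with haematology equivalents (2.11 and 2.31) and hepatobiliary abnormality tables (2.14 and 2.34). SAP 10.10.6 adds scatter plots of maximum ALT and maximum bilirubin (Figures 2.2, 2.3, 2.5 and 2.6).

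**The concern.** A worst-case or maximum display exists to show the most extreme value a participant reached. Averaging suits planned replicates, where each reading estimates the same quantity and none was prompted by another. A safety repeat is different: it is taken because the first value was abnormal, so it will tend to lie nearer to normal. Averaging the two pulls the recorded extreme towards normal, and mostly in that one direction.

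Safety is the primary objective and the groups are small, so a single flag in these tables carries weight. As the text stands, whether a crossed threshold is counted can depend on how the site or data management labelled the repeat.

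**Working it through.** **Step 1. Does the averaging rule reach the worst-case tables?** The first rule in 10.6.1 covers every derived summary statistic and exempts only listings. SAP 10.5.2 lists frequency and percentage among its descriptive summary statistics, so the counts in Tables 2.8, 2.11, 2.28 and 2.31 fall under it on a plain reading. The rule is not confined to triplicates, which section 5.2 handles. The third rule mentions the clinical-concern summary tables by name, but only for counting high and low, and gives them no exemption from the mean. So the SAP neither says outright that the mean feeds these displays nor prevents it. A programmer following the text may average first and then take the worst case.

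**Step 2. Can a repeat share the time point of the original?** Protocol 9.3.5 asks for repeats of clinically significant abnormal values. Protocol section 9 names repeat samples alongside unscheduled ones, which leaves open whether a repeat on a scheduled day counts as unscheduled. Participants are resident to Day 4 of each Part A period and to Day 17 in Part B, so a same-day redraw is practical. The outcomes by coding are:

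| How the repeat is stored | Value entering the table |
|---|---|
| Same nominal time point | Mean of first value and repeat |
| Unscheduled | First value; the repeat appears in listings only |

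**Step 3. When is a flag lost?** Let *x* be the first value, *r* one repeat and *H* the flag. The mean is (*x* + *r*)/2. A flag of the form > *H* is lost when *r* ≤ 2*H* − *x*; a flag of the form ≥ *H* is lost when *r* < 2*H* − *x*. The flags come from SAP 10.8.1. The first values and repeats are assumed, since the documents contain no data.

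| Analyte and flag | First *x* | 2*H* − *x* | Repeat *r* | Mean | Flag |
|---|---|---|---|---|---|
| Potassium > 5.5 mmol/L | 5.8 | 5.2 | 5.3 | 5.55 | kept |
| | 5.8 | 5.2 | 5.1 | 5.45 | lost |
| ALT ≥ 2 × ULN | 2.4 | 1.6 | 1.8 | 2.10 | kept |
| | 2.4 | 1.6 | 1.5 | 1.95 | lost |
| Glucose > 9 mmol/L | 9.6 | 8.4 | 8.5 | 9.05 | kept |
| | 9.6 | 8.4 | 8.0 | 8.80 | lost |

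Repeats continue until the value settles, so there may be more than one. With two repeats at the same time point, potassium 5.8, 5.3, 5.3 averages 16.4/3 = 5.47, and the flag that survived one repeat is lost.

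**Step 4. What is one lost flag worth?** Protocol 10.1 plans at most 9 participants per active dose and quotes exact 95% upper limits of 33.6% for 0/9 and 48.2% for 1/9. Both reproduce as the 0.975 quantile of Beta(*x* + 1, *n* − *x*), where *x* is now the event count; for 0/9 this is 1 − 0.025^(1/9) = 33.6%. Losing one flag therefore changes the observed rate from 1/9 (11%) to 0/9 and lowers the upper limit from 48.2% to 33.6%. No sample size, power or error rate depends on the rule.

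**The case against.** The strongest reply is that the plan already contains the harm. Its parts fare differently.

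- **Unscheduled readings are kept out of tables.** This stands for any repeat coded as unscheduled: the abnormal scheduled value stays in the table undiluted. It does not close the gap, because 10.5.2 excludes unscheduled visits, and a redraw within a scheduled inpatient day need not be one.
- **Listings show everything.** This stands. The laboratory clinical-concern listings (21, 22, 60, 61) present each value. The loss is confined to summary tables and figures, although 10.5.2 keeps listings out of the main body of the report.
- **Liver events have their own timing and displays.** This largely stands. For ALT ≥ 3 × ULN with bilirubin < 2 × ULN and INR ≤ 1.5, protocol Appendix 7 sets the repeat at 24 to 72 hours, usually a different time point. Stopping events are recorded on a dedicated CRF and summarised in Tables 2.13 and 2.33. A reader might infer that averaging would hide a liver stopping event; the documents do not support that. Even if 3.2 and 2.4 × ULN were averaged, the result of 2.8 would still exceed the SAP flag of 2 × ULN.
- **The standard shells may already use individual records.** The sponsor's display standards are not in the documents, so this can be neither confirmed nor relied on.

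A reader might also extend the point to vital signs. That fails: their only summary tables (2.19, 2.40) are change from baseline, and their clinical-concern displays are listings (32, 33, 72, 73). Nor does the closest-to-target rule create a live conflict; with no windows defined in 10.3.1 it has nothing to act on.

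**Conclusion.** The point holds for laboratory summaries only, and conditionally. Where a repeat is stored at the same nominal time point as the abnormal value, the wording of 10.6.1 allows the mean to replace the worst value in Tables 2.8, 2.11, 2.14, 2.28, 2.31 and 2.34 and in Figures 2.2, 2.3, 2.5 and 2.6. A flag that was crossed is then lost once the repeat falls far enough below the threshold, as the potassium example shows.

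The conclusion rests on two assumptions: that some repeats are stored that way, and that averaging precedes the worst-case step. The SAP settles neither. A reader might want a percentage of flags lost, but any such figure would need within- and between-person laboratory variability that the documents do not give, so none is offered. The supportable size is the consequence of a single case: 1/9 becomes 0/9. This is worth correcting because it touches the primary safety summaries and costs little, not because frequent loss has been shown.

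**What to change.** In SAP 10.6.1, limit the mean to planned replicates (triplicate ECG, pulse and blood pressure) and to the confirmatory ECGs of protocol 8.1.4. Add one sentence: laboratory worst-case, maximum, clinical-concern and hepatobiliary summary displays use the most extreme individual value at a time point, leaving out samples documented as technically invalid. Removing the closest-to-target rule would be tidy but is optional.

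The cost is a line or two of SAP text and a small programming change. The affected tables may show slightly more flagged participants. The design and sample size do not change.
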